### **C8. Study Visits.**

Screening Visit. Eligibility will be assessed. A1c will be obtained from through a blood draw (less than 1 teaspoon of blood) through a finger stick. [name] will assay the patient's sample for HbA1c using the analyzer in the UT Endocrinology Lab to assess potential eligibility. In addition, patient's weight, height, BMI, and blood pressure will be measured using the scales the appropriate scales and validated protocols. Participants will also be required to provide a list of their current medications and name and contact information of the primary care provider in event that they are randomized into the intervention arm at the baseline visit. Participants will be informed of their rights to determine who has access to their personal health information (PHI) in compliance with HIPPA regulations. As part of informed consent patients will be extensively counseled regarding all components of the treatment and control interventions to confirm their interest and willingness to participate in all component interventions prior to enrollment. After informed consent, contact and demographic information will be obtained. If a study participant has difficulty reading the informed consent or other study data collection forms, project personnel will assist. At this visit, all baseline study measures will be obtained.

Baseline Visit. Following confirmation of eligibility at the screening visit, potential participants will be scheduled for a baseline visit at the health hub. Eligible participants will be randomly assigned to one of the two arms and informed of their group assignment. Participants will be randomized to the HEAL Diabetes arm or the usual care condition. We will randomize 20-24 participants for each recruitment wave, for a goal of approximately 12 per condition. Participants will be randomized 1:1 to the two study conditions in randomly permuted blocks of size 8 using SAS random allocation. The randomization list was generated through SAS at the start of the study before randomization. The list is managed by one of the PIs. Once a participant has been determined to be eligible, the PI will assign each participant to the next open assignment on the list. We will tell

them at the Baseline visit which group they were assigned. Additionally, participants will have their first introduction to the health coaches.

Follow-up visits 1–3. Outcomes will be assessed at the end of three months (Follow-up 1), 6 months (Follow-up 2) and at one-year (Follow-up 3). All survey measures described below will be conducted at the health hubs.

Additional In-Person Visits for intervention group:

- Individual health coaching over 6 months (14 sessions total) (1 hour)
- Group support sessions (6 sessions total) (1.5 hours)
- Cooking/Nutrition classes (6 sessions total) (2 hours)

**C9. Participant Retention.** Our procedures will include the following strategies to track and retain participants: 1) collecting names, addresses, and phone numbers of relatives and friends who will usually know the participant's whereabouts; 2) contacting participants with personalized letters and cards and remembering them at special times such as birthdays and holidays; 3) maintaining phone contact with participants throughout the study; 4) setting up a tracking database with names, addresses, phone numbers, email addresses, social media page information, and projected time windows; 5) taking a case management approach for handling difficult retention cases.

Participant withdrawal. If participants withdraw from the protocol or fail to return for follow-up visits, we will continue to collect utilization and clinical data unless they withdraw consent. Data analysis will use best available follow-up weights and A1c values (closest within a window of  $\pm 3$  months from routine attendances) and end of study diabetes status for participants who discontinue the protocol. Drug intolerance, diet intolerance or poor compliance will be recorded; these patients will be included in intention-to-treat analyses.

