**Non-responders**. Data including age, gender, body weight and height, and duration of diabetes will be recorded for all patients found to satisfy recruitment criteria upon screening who decline to participate. We will record reasons for non-participation. Characteristics of non-responders will be compared with those of participants to identify any recruitment bias, assess the representativeness of study participants, and help establish generalizability of the trial findings.

**C4d. Randomization Strategy.** Eligible participants will be randomized in a 1:1 ratio using a block design with blocks of size 8. We will select the block sequence at random and fill blocks of 8 before selecting a new block. This will guarantee approximately the same number of participants in each group throughout the trial. The SAS program will be used for implementing the randomization scheme. Randomization logs will be created by [name] and uploaded to the REDCap system. The study staff will use the REDCap system to randomize patients to either the Intensive Care (Treatment) group or Enhanced Care (Control) group. Study personnel who collect and manage data will be blinded to participants' treatment assignments.

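### C4d and C8 name different assigners and routes for randomization, and the protocol never says that upcoming assignments are hidden from those who enrol

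*Combined protocol and SAP*

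**What the plan says.** C4d (Randomization Strategy) describes a system-based route. On the sequence: "Randomization logs will be created by [name] and uploaded to the REDCap system". On assignment: "The study staff will use the REDCap system to randomize patients to either the Intensive Care (Treatment) group or Enhanced Care (Control) group".

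C8 (Study Visits, Baseline Visit) describes a list-based route. The assignment step reads: "Once a participant has been determined to be eligible, the PI will assign each participant to the next open assignment on the list". Custody of that list rests with an investigator, since C8 also states: "The list is managed by one of the PIs". The sequence exists in full beforehand, because SAS produced it ahead of any assignment. C8's account of assignment does not mention REDCap. Recruitment runs in waves: "We will randomize 20-24 participants for each recruitment wave, for a goal of approximately 12 per condition". Participants are told their arm at the baseline visit.

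The sections agree on SAS, 1:1 allocation and blocks of 8.

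The sentence nearest to concealment is in C4d, and it concerns what data staff know about the arms: "Study personnel who collect and manage data will be blinded to".

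C8 puts several steps before the baseline visit. Eligibility is assessed and baseline measures are taken at screening, and candidates are counselled on both arms "to confirm their interest and willingness to participate in all component interventions prior to enrollment".

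**The concern.** A good random sequence protects the comparison only if those who decide who enters, and when, cannot see the next arm. C8 describes an investigator working from a list generated in advance. If that person, or anyone who shares sight of the list, also influences recruitment, consent, eligibility or the order in which people are presented, the arms can differ in motivation before treatment starts. There is room for such influence: the exclusion criteria in C4b include a perceived unwillingness or inability to take part, which is a judgement, and C4a leaves final eligibility to depend on later telephone contact.

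Motivation plausibly drives weight, A1c and retention. The pilot is meant to estimate effect size and retention (C4e) and to supply data for larger studies (section D), so a distorted estimate would carry forward. The baseline comparison in C11 might reveal an imbalance but would not correct it, and motivation is not among the baseline covariates listed under Other Factors. Separately, a report written from these two sections could not state which allocation method was used.

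**Working it through.** No figure in the plan is disputed. The check sets the two sections side by side and then counts how many assignments are exposed under each.

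**Side by side**

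| Item | C4d | C8 |
|---|---|---|
| Software, ratio, block size | SAS, 1:1, blocks of 8 | SAS, 1:1, blocks of 8 |
| Where the sequence sits | log uploaded to REDCap | list managed by one of the PIs |
| Who assigns | study staff | the PI |
| How | through REDCap | next open entry on the list |
| Upcoming entries hidden? | not stated | not stated |

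The first row agrees. The second can be reconciled if the list and the log are one object. The third and fourth do not match as written.

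**Does another passage supply concealment?**

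- The C4d blinding sentence covers people who collect and manage data, and concerns their knowledge of assignments. It does not say that the next entry is hidden from those who enrol.
- Sections E and G8 limit REDCap access to people approved by the data manager, and file access to those with the program director's permission. This is general data security. It does not say who may view the allocation table.
- F2d says that a Manual of Procedures will be developed and that training covers randomization. The manual is not supplied, so it can neither be credited nor faulted.

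**Exposure**

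Inputs: 72 participants (C4e), blocks of 8 (C4d and C8), waves of 20 to 24 (C8).

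- Plan's own figure: 8 per month × 9 months = 72, which is 72 / 8 = 9 complete blocks.
- C8 as written, entries the list holder can see for one wave: 20 / 72 = 28% to 24 / 72 = 33%.
- C8 as written, over the whole trial: 72 / 72 = 100%, because the list was generated in advance.
- C4d, if the allocation table is hidden from those who enrol: none is visible from the list.

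The contrast comes from access to the list. The size of any resulting bias cannot be estimated from the documents.

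**The case against.** The best reply is that this is one process described twice: the SAS list is the uploaded log, and a PI, as a member of the study team, operates REDCap. C8 is silent on REDCap rather than excluding it, and the name of the log's creator is masked and could be that PI. This is possible, and for that reason the two sections should not be called irreconcilable. But the text does not say it, and even the merged reading leaves unstated who can see upcoming entries.

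The second reply is that C8 already orders the steps sensibly. Eligibility, counselling and baseline measures precede the baseline visit, F2a requires a signature before randomization, and taking the next open entry leaves no choice of entry once a person is presented. That stands, and it narrows the opportunity. It does not govern who is presented, or when, by someone who knows what comes next.

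Three stronger readings are tempting and are not supported.

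- A reader might infer that allocation has been steered, or that the PI chooses arms. Nothing shows this. No passage makes the list holder responsible for recruitment, consent or eligibility.
- A reader might infer that the fixed block size makes assignments guessable and should change. That needs someone who both knows past assignments and influences enrolment, and the documents identify no such person.
- A reader might want each whole wave enrolled before its first assignment. At the planned 8 per month, a wave takes 20 / 8 = 2.5 to 24 / 8 = 3 months. If accrual is steady, early participants could wait about that long between baseline measures and randomization. Release person by person avoids that wait.

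F2a places consent at screening and G1 at the start of the baseline appointment. These should be aligned, but as a separate wording matter: no passage puts consent after assignment.

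**Conclusion.** The point holds as a gap in the written design. C4d and C8 name different assigners and routes, and neither they nor any other supplied section says that upcoming assignments are hidden from those who recruit, consent or confirm eligibility. C8 goes further than leaving a detail out. It sets down a specific and weaker procedure, an investigator-held list in an open-label trial, while C4d already offers a better one.

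The exposure under C8 is all 72 entries, visible to at least one investigator. That rests on reading C8 literally, with the person who manages the list able to read it. Whether exposure becomes bias depends on that person's part in enrolment, which is not stated, and on a manual that was not available. The supported conclusion is that concealment is undocumented, not that it failed. It should be fixed, and the fix is cheap.

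**What to change.** 1. Make REDCap the only allocation route, and replace the PI-list step in C8 with wording that matches C4d.
2. Restrict the allocation table so that nobody who recruits, takes consent or confirms eligibility can view it, including a PI acting in any of those roles. State this in C4d.
3. Release each participant's arm only after that participant's eligibility, consent and baseline measures are recorded.
4. For anyone already randomized, record which route was used and who could see the list. The documents do not say how many people this covers.
5. As a separate edit, align F2a and G1 on when consent is taken.

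The cost is protocol wording and REDCap access settings, since REDCap is already planned. Sample size, block size, visits and treatment are unchanged. A new list would be needed only if people who enrol prove to have seen the existing one.

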**Procedures for Involuntary or Voluntary Study Discontinuation**

Phase 1-Intensive Preparation for Change. If participants are removed from the study or voluntarily stop participation, nothing will occur since they have only received educational instruction and no other study procedures. Data collected from their participation will be analyzed using the "intention to treat" principle.

Phase 2-Total Diet Replacement. If participants are removed from the study or choose not to continue, participants will be advised to follow up with their primary care provider and resume their diabetes and antihypertensive medication, as well as continue healthier diet and lifestyle changes. Participants will be informed that they can continue to receive Neighborhood Health Hub (NHH) services, including health coaching and group activities and education. Participants can also speak with the medical director and/or the PI if they have any questions about their ongoing care. In addition, participants may elect to have their glucose, blood pressure, and weight checked. Data collected from their participation will be analyzed using the "intention to treat" principle.

Phase 3-Food Reintroduction. If participants are removed from the study or choose not to continue, participants will be advised to follow up with their primary care provider and resume their diabetes and antihypertensive medication, as well as continue healthier diet and lifestyle changes. Participants will be informed that they can continue to receive Neighborhood Health Hub (NHH) services, including health coaching and group activities and education. Participants can also speak with the medical director and/or the PI if they have any questions about their ongoing care. If participants proceed with their 6-month assessment, data collected will be analyzed using the "intention to treat" principle.

Phase 4- Weight Loss Management. If participants are removed from the study or choose not to continue, participants will be advised to follow up with their primary care provider and resume their diabetes and antihypertensive medication, as well as continue healthier diet and lifestyle changes. Participants will be informed that they can continue to receive Neighborhood Health Hub (NHH) services, including health coaching and group activities and education. Participants can also speak with the medical director and/or the PI if they have any questions about their ongoing care. Data collected from their participation will be analyzed using the "intention to treat" principle. If participants proceed with their 12-month assessment, data collected will be analyzed using the "intention to treat" principle.

**C10. Outcome Measures. Outcome Measures.** As shown in **Table 3**, our primary *biological outcomes* assessing effectiveness (Aim 2) replicate the main outcome measures of the DIRECT study. **Table 3** also details our secondary metabolic, patient-reported, and sustainability outcomes. To assess cost-effectiveness for Aim 1, we will calculate incremental cost of delivering the intervention to the study group compared to the control group by tracking all the program implementation costs, net of one-time costs associated with developing study materials or other costs that would not be expected to be incurred if the intervention were repeated or scaled up.

**Table 3: Outcome Measures**

Outcome Measures	Measurement	Schedule
Primary biological outcomes (Aim 2)		
Body weight (kg)	Body weight will be measured without shoes in regular clothes using calibrated scales (Befour Model: WH1061)	Baseline, 3-, 6-, and 12-month visits
		Weekly
Blood pressure (mm Hg)	Systolic and diastolic blood pressure using automated cuffs (Omron Model: HEM-907) using a validated protocol  and number of blood pressure medications by patient report supplemented by medical record review	Baseline, 3-, 6-, and 12-month visits
A1c (%)  and diabetes remission 	Metabolic assessments obtained using standard protocols with diabetes remission defined as A1c < 6.5% after at least 2 months off all antidiabetic medications except GLP-1 agonists and SGLT-2 agonist medications, from baseline, months 6 & 12	Baseline, 6-, and 12-month visits
Secondary metabolic and patient-reported outcomes (Aims 1 and 2)		
Self-efficacy	129,130 Stanford Diabetes Self-Efficacy Scale	Baseline, 6-, and 12-month visits
Diabetes self-management	Two (out of six total) subscales of the revised Summary of Diabetes Self-Care Activities questionnaire for general diet and exercise	Baseline, 6-, and 12-month visits
Secondary sustainability outcomes (Aim 1)		
Program retention (operational sustainability)	Proportion of patients retained in study at each follow-up visit calculated by dividing the number who completed follow-up at each interval by the number expected.	3-, 6-, and 12-month visits
Cost effectiveness of the multicomponent intervention (financial sustainability)	Cost-effectiveness may be calculated using method employed by DiRECT  and recommended by Centers for Disease Control and Prevention.  Incremental total costs per patient related to primary outcomes of body weight (cost per additional kg weight loss), A1c (cost per additional unit A1c reduction), and diabetes remission (cost per additional diabetes remission) at one year calculated using an intention to treat analysis. Effectiveness measured as quality adjusted life years (QALYs) using EQ-5D. 	Following completion of data collection

**Other Factors.** Covariates will be measured at baseline. These will include demographic characteristics, marital status, education level, insurance, chronic conditions, and SDOH (using electronic health record data collected on all Health Hub clients), and health literacy. At baseline, 6-, and 12-month visits, we will assess prescribed medications. Exposure to each component intervention will be assessed using health coach attendance logs.

**C11. Analysis.** We will evaluate the extent to which the program was implemented according to the protocol, examine if all components of the intervention were delivered in a standardized and reproducible format, and summarize the trial as a flow diagram following Consolidated Standards of Reporting Trials (CONSORT) guidelines. Patient characteristics will be compared between study groups to assess integrity of the random assignment process. Data will be presented as means and standard deviations for continuous variables and as frequencies and percentages for categorical variables. Results will be analyzed based on intention-to-treat.

For Aim 2, we will use baseline, 6-, and 12-month follow-up data to compare differences between treatment and control group means in continuous primary biological outcomes (body weight, blood pressure, and A1c) and secondary patient-reported outcomes (self-care activities related to general diet and exercise). We will use the MIXED procedure of SAS because this is a parallel groups trial with repeated measures assessed over time. In the context of repeated measures ANOVA, we will use t-tests within group to detect change from baseline to 12-months (Follow-up 3) and t-tests between groups to detect the effect of the treatment on the various outcome variables at 12-months. While the preceding hypothesis tests are *a priori* and not adjusted, other comparisons at the intermediary assessments will be adjusted using the Bonferroni method. To examine a difference in the proportion of patients who achieved diabetes remission at 12-month, we will use a chi-square test.

For Aim 1, we will assess intervention operational sustainability as detailed above and in **Table 3**. Based on MODEL study experience providing MI-based HC and TM interventions, we hypothesize that operational sustainability will be high with 12-month program retention rates of approximately 85-90%.

We will assess financial sustainability using cost-effectiveness analysis to estimate the incremental cost of providing the intervention compared with the control group as detailed in **Table 3** above. Our analysis will be

conducted from the payer perspective. Based on DiRECT study experience, we hypothesize that the *HEAL Diabetes* intervention will be cost-effective when compared with control.

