**Table 2. Study Timeline, Intervention Phases and Components, and Study Procedures**

Month(s)	Study Procedures	Treatment Group (Intervention Phases and Components)	Control Group (Intervention Phases and Components)
	Screening		
1	Baseline Visit (Randomization)	Phase 1 -Intensive Preparation for Change: 1) Two (introductory and kickoff) health coach and nutritionist or dietitian co-led support group sessions, 2) Health coaching, 3) Tailored motivational text messaging	Phase 1 -Education: One traditional diabetes education session led by a pharmacist or nutritionist/registered dietitian
2-4	Follow-up Visit 1 (Month 3)	Phase 2 -Total Diet Replacement: 1) Total diet replacement for months 2-4 using tailored healthy food boxes with recipes, 2) Health coaching, 3) Tailored motivational text messaging, 4) Coach-led support groups, 5) Monthly cooking classes, 6) Physician-supervised medication discontinuation	Phase 2 -Partial Diet Replacement: Partial diet replacement for 3 months using grocery store produce vouchers
4-6	Follow-up Visit 2 (Month 6)	Phase 3 -Food Reintroduction: 1) Health coach-led individual or group grocery store tours with individual patient reminders, 2) Health coaching, 3) Tailored motivational text messaging, 4) Coach-led support groups, 5) Monthly cooking classes	Phase 3 -Food Reintroduction: No additional activities
6-12	Follow-up Visit 3 (Month 12)	Phase 4 -Weight Loss Maintenance: 1) Health coaching, 2) Tailored motivational text	Phase 4 -Weight Loss Maintenance: No additional activities

		messaging, 3) Coach-led support groups, 4) Monthly cooking classes	
--	--	---	--

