Blood glucose will be monitored weekly at the UTHSC Health Hub months 2 through 4 (e.g., during the Total Diet Replacement phase) and periodically thereafter. Health Coaches and the UTHSC Health Hub medical director should encourage participants to continue any glucose monitoring recommended by their primary care physician or diabetes doctor and to contact their doctor and/or the UTHSC Health Hub Medical Director for blood glucose levels below 70 or above 300. Blood pressure will be monitored weekly at the UTHSC Health Hub for the 2nd – 4th months of the study (e.g., during the Total Diet Replacement phase) and periodically thereafter. Health Coaches and the UTHSC Health Hub medical director should encourage any self-monitoring recommended by their primary care physician. Advise participants to notify their healthcare provider and the Health Hub Medical Director for systolic blood pressure greater than 160 or diastolic BP greater than 100 with symptoms (acute vision changes, headache, chest pain, etc.) or systolic blood pressure greater than 180 or diastolic greater than 110 (regardless of symptoms). Advise participants to immediately call emergency medical services and seek emergent medical care for blood pressure readings 180/110 or higher AND symptoms of chest pain, shortness of breath, numbness, weakness, change in vision, difficulty speaking, or severe headache. In the three months of total diet replacement, participants should be seen at least once a week and should be offered blood glucose and blood pressure checks to assess for hyperglycemia, hypoglycemia, and/or hypertensive episodes. HEAL Diabetes Program Participant Medication Reduction/Discontinuation Instructions will be included in the intervention group's toolkits. Study personnel, including health coaches and the medical director will emphasize instructions for monitoring for adverse events related to blood pressure or blood glucose. Procedures for monitoring blood glucose and blood pressure will be included and further detailed in the Manual of Procedures (MOP).

Adverse events related to medication discontinuation are unlikely but may include hyperglycemia and hypertension. We will monitor those in the intervention group regularly for adverse events related to medication

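### C11 names only baseline, 6 and 12 months for the Aim 2 mixed model, although weight and blood pressure are also scheduled at month 3; stating whether month 3 enters is a minor, cheap improvement

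*Combined protocol and SAP*

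**What the plan says.** C11 covers all continuous Aim 2 outcomes in one sentence: "we will use baseline, 6-, and 12-month follow-up data to compare differences between treatment and control group means in continuous primary biological outcomes". The model is SAS MIXED. The between-group comparison at 12 months is a priori and unadjusted. Comparisons at intermediate assessments, in the plural, get a Bonferroni adjustment; the number of comparisons is not stated.

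Table 3 gives weight and blood pressure the schedule "Baseline, 3-, 6-, and 12-month visits". A1c and the patient-reported outcomes have "Baseline, 6-, and 12-month visits". C8 makes month 3 the first follow-up at which outcomes are assessed, and Table 2 lists that visit in the study-procedures column shared by both arms. The visit has one stated analytic use, retention: "Proportion of patients retained in study at each follow-up visit". No section gives the month-3 weight or blood pressure a role in the effect model.

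Two other passages bear on the point. For participants who discontinue, C9 continues clinical data collection unless consent is withdrawn, and uses the best available weight and A1c closest within three months either side. Other Factors, after Table 3, says "At baseline, 6-, and 12-month visits, we will assess prescribed medications", whereas the blood pressure row of Table 3 puts the number of blood pressure medications on the schedule that includes month 3.

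**The concern.** A likelihood-based mixed model allows for dropout that depends on values in the model. If month 3 is left out, a participant who attends at month 3 and is not seen again contributes only a baseline value, and the model cannot use the early response that may explain the departure. If poor early responders leave one arm more than the other, the 12-month difference is biased. When they leave the treatment arm, the bias favours treatment.

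Such a pattern is conceivable here. Table 2 has food boxes in the treatment arm in months 2-4 followed by food reintroduction, while the control arm has no further activities after its vouchers. The documents state no dropout mechanism, so this is an inference.

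Separately, C11's own list leaves only one intermediate follow-up, month 6, while its multiplicity sentence uses the plural. A programmer could reasonably build the model either way.

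**Working it through.** **The plan's own figure.** C4e: 72 x (1 - 0.15) = 61.2, so its figure of about 61 completers reproduces, leaving about 11 non-completers. Month 3 can add information only for those seen at month 3 who later go missing. If half of the dropout falls in months 3-6, that interval holds 0.5 x 10.8 = 5.4, about 5 people; if a third, 3.6, about 4.

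**Complete data.** With a separate mean for each arm and visit and an unstructured covariance, adding month 3 leaves the 12-month contrast unchanged. Any gain comes through dropout alone.

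**Assumptions, none in the documents.** SD of weight change 5, 7 and 9 kg at months 3, 6 and 12. Correlations (3-6, 6-12, 3-12) of 0.85/0.85/0.65, 0.75/0.80/0.65 and 0.85/0.85/0.75, with a lower case in which the 3-12 correlation is 0.5. Total dropout 15% in each arm. In months 3-6 it is driven by month-3 change and in months 6-12 by month-6 change, with an odds ratio of 1.6 to 3.7 per SD of poorer response. Control dropout is random unless stated.

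**Standard error.** With SD 9 kg: sqrt(2 x 81/36) = 2.12 kg with everyone observed, and sqrt(2 x 81/30.6) = 2.30 kg with completers only (36 x 0.85 = 30.6). About 2.2 kg is used below.

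**Bias in the 12-month weight difference without month 3** (large-sample maximum likelihood; negative overstates the treatment effect):

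| Dropout pattern at 15% | Bias, kg |
|---|---|
| One third each in months 0-3 (random), 3-6 and 6-12 | -0.14 to -0.42 |
| Same, 3-12 correlation 0.5 | -0.12 to -0.29 |
| Nobody leaves before month 3, half in 3-6, half in 6-12 | about -0.20 to -0.58 |
| As the row above, half of leavers still have a 12-month weight | -0.10 to -0.28 |
| Nobody leaves before month 3, odds ratio 2.7 in treatment and 1.6 in control | -0.20 to -0.25 |
| Three-way split, odds ratio 2.7 in treatment and 1.6 in control | -0.15 to -0.17 |
| Random, or the same pattern in both arms | about 0 |

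Where dropout depends on measured values, including month 3 brings the bias to within about 0.02 kg of zero. If dropout instead follows unmeasured weight between visits, month 3 removes only about 60-70% of it (no early leavers: -0.28 to -0.74 kg becomes -0.08 to -0.30 kg).

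**In standard-error units.** 0.42/2.2 = 0.19 for the three-way split and 0.58/2.2 = 0.26 for the upper case. In simulated trials of 36 per arm with no early leavers, coverage of the 95% interval is 94.1-94.9% without month 3 and 94.9-95.2% with it. Root mean squared error falls from 2.24-2.28 to 2.19-2.21 kg.

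**A second set-up.** With SDs of 5/7/8 kg and a true difference of 9 kg, adding month 3 lowers the standard error by about 0.2-3% when dropout is spread over the year. The arm-specific bias without month 3 is about 0.2-0.6 kg. It reaches 0.5-1.3 kg only if all dropout falls in months 3-6.

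**Blood pressure.** Assumed: systolic SD 15 mmHg, between-visit correlations 0.4-0.6, correlation with weight change 0.2-0.4, dropout driven by weight, nobody leaving before month 3. The bias is -0.08 to -0.56 mmHg without month 3 and -0.01 to -0.29 with it, against a standard error of about 3.8 mmHg. At most that is 0.56/3.8 = 0.15 of a standard error, and it is only partly removed.

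**The case against.** The strongest case against is that this hardly matters. N is a pragmatic choice for a pilot, the bias is a fraction of a standard error, coverage barely moves, and the larger figures need two favourable conditions: nobody leaving before month 3, and response-driven dropout in one arm only. The documents point the other way on the first. The discontinuation procedures begin in Phase 1, retention is counted at month 3, and C6 plans interviews with early drop-outs; month 3 cannot help those people. C9 also retrieves later weights for some leavers. All of this stands, and it is why the range for spread dropout should be the one read first and why the point is rated minor.

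A reader might infer that C11 deliberately excludes month 3. The documents do not support that. The omission is by silence, in one sentence covering several outcomes whose common visits are exactly baseline, 6 and 12 months, and the plural for intermediate assessments points the other way.

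A reader might also infer that the 12-month comparison is seriously biased as planned. Nothing in the documents shows arm-specific dropout, and even when it is assumed the effect is small.

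Finally, C11 does not name a covariance structure. The figures describe an unstructured model, which may not be the one intended.

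**Conclusion.** The inconsistency is real: month-3 weight and blood pressure are scheduled in both arms, and C11 gives them no stated place in the effect model. The consequence is small and conditional. At 15% dropout driven by response in the treatment arm only, omitting month 3 shifts the 12-month weight difference by about -0.1 to -0.4 kg when dropout is spread over the year, and by up to about -0.6 kg if nobody leaves before month 3, which is roughly a quarter of a standard error at most. The shift is about zero if dropout is random or alike in both arms, and smaller if the arms differ only in part or later weights are retrieved. For blood pressure it is smaller relative to its standard error and only partly removed. These sizes rest on assumed SDs, correlations and dropout patterns. This is a minor, optional improvement justified by its low cost; it does not call the 12-month analysis into question.

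**What to change.** Reconcile C11 with Table 3 and C8 in a sentence or two:

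- For weight and measured systolic and diastolic blood pressure, fit the MIXED model on baseline, 3, 6 and 12 months with unstructured covariance. Keep the 12-month between-group contrast as the unadjusted a priori test.
- Let month 3 enter the likelihood without being tested. If a month-3 comparison is reported, count it in the Bonferroni family and state the family's size.
- Leave A1c, the patient-reported outcomes and medication counts at baseline, 6 and 12 months, and align the Table 3 medication entry with Other Factors.
- Do not add the weekly weights. C5g ties weekly contact to diet replacement ("In the three months of total diet replacement, participants should be seen at least once a week"), total diet replacement is a treatment-arm component, and the documents do not show that controls have weekly values.
- Under C9, state that one measured value may not serve two visits. A weight at month 9, for example, lies within three months of both month 6 and month 12.

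Cost: no new data. The covariance grows from 3 x 4/2 = 6 to 4 x 5/2 = 10 parameters; in simulation at 36 per arm with random dropout, coverage stayed at 94.8-95.2%. Testing month 3 would cost power at month 6. As an illustration only, if the family grew from one comparison to two at an assumed 0.05, a test with an assumed 80% power would fall to 1 - Phi(2.241 - 2.802) = 0.71. Leaving month 3 untested avoids this.
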